The summarization of AEs will include TEAEs. TEAEs and SAEs will be summarized by system organ class (SOC), severity, and relationship to study drug for each treatment group. These AE summaries will include cumulative incidence (percent of patients experiencing the AE) and patient-year adjusted incidence rates. If appropriate, absolute and relative risk differences will be calculated using both cumulative incidence and incidence rates. Deaths, withdrawal from study treatment due to AEs, and withdrawal from the study due to AEs will each be summarized by treatment group.

Clinical safety laboratories, including hematology, blood chemistry, coagulation, HbA_{1C}, glucose, and urinalysis; PE findings; vital signs; ECG readings; and weight will be summarized by the value and by change from baseline in the value (where appropriate) at each post baseline time point.

Hepatic Safety

For liver-associated enzymes and TB, the number and percent of patients with abnormal values for ALT, AST, and TB will be summarized. Hy's law criteria ($\geq 3 \times$ ULN for either ALT or AST, with accompanying TB $> 2 \times$ ULN in the absence of other known causes) will also be applied to the data; any potential Hy's law cases will be listed separately. For patients with Gilbert's disease, conjugated (direct bilirubin) will be used for the evaluation.

Musculoskeletal Safety

AEs of muscle-related symptoms will be summarized by treatment group. In addition, the number and percent of patients with abnormal CK values will be summarized.

Diabetes/Hyperglycemia

Cases of new onset of diabetes will be recorded as AEs and will be summarized using the appropriate SOC. These events will be summarized by severity and relationship to study drug for each treatment group.

Renal Safety

Baseline eGFR and values of CK will be summarized by treatment group and by baseline eGFR categories. Shift tables of eGFR category from baseline over the study, will be provided by treatment group. Finally, muscle-related AEs will be summarized by treatment group and by baseline eGFR category.

Neurocognitive Events

Neurocognitive events will be identified and evaluated by routine safety monitoring of PE findings and AEs. Summarization of neurocognitive events will occur using prespecified Medical Dictionary for Regulatory Activities (MedDRA) terms and will be performed by treatment group.

Clinical endpoints

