8. Liver disease or dysfunction, including:
 - Positive serology for hepatitis B surface antigen (HBsAg) and/or hepatitis C antibodies (HCV-ABV_{ivi}) at Week -5 (Visit S1).
 - Alanine aminotransferase (ALT), aspartate aminotransferase (AST) $\geq 2 \times$ ULN, and/or total bilirubin (TB) $\geq 1.2 \times$ ULN at Week -5 (Visit S1). If TB $\geq 1.2 \times$ ULN, a reflex indirect (unconjugated) bilirubin will be obtained and if consistent with Gilbert's disease or if the patient has a history of Gilbert's Disease, the patient may be enrolled in the study.

Note: At the discretion of the investigator, a single repeat of ALT, AST, and/or TB may be completed prior to randomization. For those patients who have a repeat ALT and/or AST, the repeat value will be used to determine eligibility. Also, if test for hepatitis C antibody is positive, but optional reflexive test for hepatitis C ribonucleic acid (RNA) is negative, patient can be enrolled.

9. Gastrointestinal conditions or procedures (including weight loss surgery; eg, Lap-Band[®] or gastric bypass) that may affect drug absorption.
10. Hematologic or coagulation disorders or a hemoglobin (Hgb) level <10 g/dL at Week -5 (Visit S1)
11. Persistent poor compliance or lack of tolerance with single-blind, placebo study drug (ie, ingesting <80% average of planned doses) assessed at the T1 visit prior to randomization.
12. Active malignancy, including those requiring surgery, chemotherapy, and/or radiation in the past 5 years. Non-metastatic basal or squamous cell carcinoma of the skin and cervical carcinoma in situ are allowed.
13. Unexplained creatine kinase (CK) >3 × ULN at screening up to randomization (ie, not associated with recent trauma or physically strenuous activity). Patients with an explained CK elevation must have single repeat CK ≤3 × ULN prior to randomization.
14. History within the last 2 years of drug, alcohol, amphetamine and derivatives, or cocaine abuse. Patients taking amphetamine derivatives for medical reasons such as attention deficit disorder or taking prescription opioids or other meds for chronic pain that have been stable, without evidence of abuse, and prescribed by and under the care of a health care practitioner can be enrolled after evaluation by the Investigator.
15. Blood donation, participation in a clinical study with multiple blood draws, major trauma, blood transfusion, or major surgery with or without blood loss within 30 days prior to randomization.

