10.1.6. Clinical Laboratory Tests

10.1.6.1. Laboratory Parameters (Safety)

Patients will be in a seated position during the blood collection. Clinical laboratory parameters and tests will include those listed in [Table 3-Table 4](#). Collection schedule, schedule of laboratory parameters by visit, and instructions are in the Clinical Laboratory Manual provided by Central Laboratory.

Table 4: Clinical Laboratory Parameters (Safety)

Clinical Laboratory Test	Clinical Laboratory Test

Hematology
 
 • Hematocrit (Hct) • Hemoglobin (Hgb) • Mean corpuscular hemoglobin (MCH) • Mean corpuscular hemoglobin concentration (MCHC) • Mean corpuscular volume (MCV) • Platelet count • Red blood (RBC) cell count • White blood (WBC) cell count with differential (absolute and %) 	
Blood Chemistry (serum, fasting)
 
 • Albumin (Alb) • Alkaline phosphatase (Alk-P) • Alanine aminotransferase (ALT; SGPT) • Aspartate aminotransferase (AST; SGOT) • Blood urea nitrogen (BUN) • Calcium (Ca) • Carbon dioxide (CO₂) • Chloride (Cl) • Creatinine • Creatine kinase (CK) • Glucose • Lactate dehydrogenase (LDH) • Phosphorus • Potassium (K) • Sodium (Na) • Total and direct bilirubin (TB) • Total protein • Uric acid

Urinalysis (Dipstick)
 
 • Clarity • Bilirubin • Color • Glucose • Ketones • Leukocyte esterase • Nitrite • Occult blood • pH • Protein • Specific gravity • Urobilinogen • Urine Pregnancy in females of child bearing potential 	

Table 4: Clinical Laboratory Parameters (Safety)

Clinical Laboratory Test	Clinical Laboratory Test

Urinalysis (Microscopic)-only if urine dipstick abnormal
 
 • Bacteria • Casts • Crystals • Epithelial cells • Red blood cell (RBC) • WBC 	
Coagulation – all patients at Visit S1; only in patients receiving vitamin K antagonists at Visit T1 and 3 to 5 days post Visit T1 using local or central lab
 
 • Prothrombin time (PT) • International normalized ratio (INR)

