10.2.11.3.2. Hepatic Function

Hepatic function will be monitored throughout with the clinical safety labs. More detailed investigation will occur if the safety clinical laboratory results are 3 times or more than the ULN).

If at any time after randomization a patient experiences a new ALT and/or AST $>3 \times$ ULN, the patient will undergo repeat confirmatory LFT assessment as soon as is reasonably possible, preferably within 3 to 7 days of the laboratory result becoming available.

Repeat LFT assessment will include: 1) measurement of ALT, AST, alkaline phosphatase, total and direct bilirubin, prothrombin time (PT)/international normalized ratio (INR), eosinophil count, CK, antihepatitis A virus (total), HBsAg (confirmation of screening measurement), HCV (confirmation of screening measurement), and anti-cytomegalovirus/immunoglobulin M; 2) history of concomitant medication use; 3) history of exposure to environmental chemical agents, including ethanol; and 4) query for related symptoms. Additionally, further testing such as liver ultrasound or magnetic resonance imaging (MRI) scanning may be warranted to rule out additional pathology depending on clinical presentation and should be discussed with the Sponsor personnel or the authorized Medical Monitor.

- If repeat LFT assessment confirms ALT and/or AST $>3 \times$ ULN, consideration should be given to withdrawing the patient and administering no further doses of study drug. At the investigator's discretion, study drug may be interrupted and the patient rechallenged with study drug after LFTs have returned to baseline levels.
- If repeat LFT assessment confirms ALT and/or AST $>5 \times$ ULN, patient should be withdrawn from study drug treatment, but will be asked to continue to be followed for safety using the protocol-specified visit schedule (see [Section 8.3](#)) or more frequently if deemed appropriate by the Investigator.
- If repeat LFT assessment confirms ALT and/or AST $>3 \times$ ULN in addition to any of the following, the patient should be given no further treatment with study drug, but will be asked to continue to be followed for safety using the protocol-specified visit schedule (see [Section 8.3](#)) or more frequently if deemed appropriate by the Investigator:
 - TB $>2 \times$ ULN (will be fractionated if $>2 \times$ ULN and for those with Gilbert's Disease $2 \times$ ULN conjugated (direct) bilirubin will be evaluated)

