11. STATISTICS

11.1. General Considerations

The statistical analyses described in this section will be performed as further outlined in a separate Statistical Analysis Plan (SAP). The SAP will supersede the protocol in the event of any differences between the 2 documents in relation to data analysis, and the protocol will be amended if appropriate. The SAP will be included as an appendix in the clinical study report for this protocol.

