11.7. Safety Analysis

The summarization of AEs will include TEAEs, defined as any unfavorable and unintended sign, symptom, or disease temporally associated with the use of the investigational product, whether or not related to the product. TEAEs and SAEs will be summarized by SOC, severity, and relationship to study drug for each treatment group. These AE summaries will include cumulative incidence (percent of patients experiencing the AE) and patient-year adjusted incidence rates. If appropriate, absolute and relative risk differences will be calculated using both cumulative incidence and incidence rates. Deaths, withdrawal from study treatment due to AEs, and withdrawal from the study due to AEs will each be summarized by treatment group.

Clinical safety laboratories, including hematology, blood chemistry, coagulation, HbA_{1C}, glucose, and urinalysis; PE findings; vital signs; ECG readings; and weight will be summarized by the value and by change from baseline in the value (where appropriate) at each post baseline time point.

Hepatic Safety

For liver-associated enzymes and TB, the number and percent of patients with abnormal values for ALT, AST, and TB will be summarized. Hy's law criteria ($\geq 3 \times$ ULN for either ALT or AST, with accompanying TB $> 2 \times$ ULN (conjugated [direct] if Gilbert's Disease) in the absence

of other known causes) will also be applied to the data; any potential Hy's law cases will be listed separately.

Musculoskeletal Safety

AEs of muscle-related symptoms will be summarized by treatment group. In addition, the number and percent of patients with abnormal CK values will be summarized.

Diabetes/Glycemia

Cases of new onset of diabetes will be recorded as AEs and will be summarized using the appropriate SOC. These events will be summarized by severity and relationship to study drug for each treatment group.

Renal Safety

Baseline eGFR and values of CK will be summarized by treatment group and by baseline eGFR categories. Shift tables of eGFR category from baseline over the study, will be provided by treatment group. Finally, muscle-related AEs will be summarized by treatment group and by baseline eGFR category.

Neurocognitive Events

Neurocognitive events will be identified and evaluated by routine safety monitoring of PE findings and AEs. Summarization of neurocognitive events will occur using prespecified MedDRA terms and will be performed by treatment group.

Clinical endpoints

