### 19.4. LABORATORY EVALUATIONS

Results from the central laboratory will be included in the reporting of this study for Hematology, Blood Chemistry, Lipids, Coagulation, HbA1c, hsCRP and Urinalysis. A list of laboratory assessments to be included in the outputs is included in Protocol, [Section 10.1.6.1](#).

Presentations will use SI Units and conventional units.

Quantitative laboratory measurements reported as “< X”, i.e. below the lower limit of quantification (BLQ), or “> X”, i.e. above the upper limit of quantification (ULQ), will be converted to X for the purpose of quantitative summaries, but will be presented as recorded, i.e. as “< X” or “> X” in the listings.

The formula to calculate eGFR is:  $eGFR = 186 \times (\text{Creatinine} / 88.4)^{-1.154} \times (\text{Age})^{-0.203} \times (0.742 \text{ if female}) \times (1.210 \text{ if black})$ , where creatinine is in mmol/L.

Summaries for all lab results, including unscheduled visit values, will be included for below analyses:

- Observed and change/percent change from baseline by visit (for quantitative measurements).

[REDACTED]

Version Number: 1.7  
 Version Date: 21Mar2018

[REDACTED]

- Observed and change/percent change from baseline for HbA1c and glucose by history of diabetes and visit.
- Shift from baseline by visit according to normal ranges.
- Shift from baseline according to normal ranges for HbA1c and glucose by history of diabetes and visit.
- eGFR and values of CK will be summarized by treatment group and by baseline eGFR categories (low, normal, high).
- Potential Hy’s law cases (>3 × ULN for ALT and/or AST with concurrent Total Bilirubin >2 × ULN) will be tabulated listed.
- Laboratory abnormalities in parameters of interest

ALT or AST (> 3x ULN , >5xULN)

TB (>2x ULN)

CK (> 5x ULN) and (>10x ULN)

Fasting Blood Glucose (≤50 mg/dL, ≥126 mg/dL) by history of diabetes

HbA1c (≥6.5%) by history of diabetes

Creatinine (change from baseline for >1 mg/dL )

eGFR (< 15 mL/min/1.73m^2, 15 –< 30 mL/min/1.73m^2)

Hgb (decrease from baseline for ≥2 g/dL)

Hgb (<8 g/dL)

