**19.4.1. LABORATORY REFERENCE RANGES AND MARKEDLY ABNORMAL CRITERIA**

Quantitative laboratory measurements will be compared with the relevant laboratory reference ranges in SI units and categorized as:

- Low: Below the lower limit of the laboratory reference range.
- Normal: Within the laboratory reference range (upper and lower limit included).
- High: Above the upper limit of the laboratory reference range.

In addition to the high and low quantitative laboratory assignments, Hy’s law criteria (≥3 × ULN for either ALT or AST, with accompanying total bilirubin >2 × ULN in the absence of other known causes) will be used to identify potential Hy’s law cases.

[REDACTED]

Version Number: 1.7  
 Version Date: 21Mar2018

[REDACTED]

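### SAP 19.4 and 19.4.1 define potential Hy's law cases on total bilirubin for all patients and omit the protocol's direct-bilirubin rule for Gilbert's disease, so these patients may be misclassified

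*SAP*

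**What the plan says.** **Eligibility.** Exclusion criterion 8 (Protocol 6.2.2) bars total bilirubin at or above 1.2×ULN at screening. It makes an exception after a reflex indirect bilirubin test: "if consistent with Gilbert's disease or if the patient has a history of Gilbert's Disease, the patient may be enrolled in the study". No upper limit on total bilirubin is given for these patients.

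**Protocol analysis rule.** Section 11.7 writes the exception into its Hy's law criterion: "conjugated [direct] if Gilbert's Disease". The synopsis, at the end of its hepatic safety paragraph, says: "For patients with Gilbert's disease, conjugated (direct bilirubin) will be used for the evaluation". Section 10.2.11.3.2 takes the same approach in on-study monitoring, where for these patients "conjugated (direct) bilirubin will be evaluated".

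**SAP.** Section 19.4 tabulates potential Hy's law cases as values above 3×ULN "for ALT and/or AST with concurrent Total Bilirubin >2 × ULN". Section 19.4.1 gives a second criterion, "with accompanying total bilirubin >2 × ULN in the absence of other known causes". Section 19.4 also lists total bilirubin above 2×ULN among the laboratory abnormalities of interest. Gilbert's disease does not appear anywhere in the SAP text.

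**Precedence.** Protocol 11.1: "The SAP will supersede the protocol in the event of any differences between the 2 documents in relation to data analysis".

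**The concern.** In Gilbert's disease total bilirubin can be raised through the unconjugated fraction without liver injury. That is why the protocol looks at the direct fraction in these patients. An analysis programmed from the SAP would not do so, and it could misclassify a patient in either direction.

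- **False flag.** A patient whose total bilirubin stays above 2×ULN from unconjugated bilirubin alone, and who has an ALT or AST value above 3×ULN for any reason, meets the SAP 19.4 definition.
- **Missed case.** Under SAP 19.4.1 the same patient could be set aside because Gilbert's disease is another known cause, even if direct bilirubin has truly risen. The protocol's rule avoids this by keeping the patient under assessment on the informative fraction.

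Potential Hy's law cases are expected to be few, so any entry in that table will be examined one by one. The definition should be settled before that happens.

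**Working it through.** The documents state no figure for this point, so there is nothing to reproduce. The check is a comparison of texts, followed by a sense of scale.

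**Step 1. The definitions side by side**

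| | Synopsis | Protocol 11.7 | SAP 19.4 | SAP 19.4.1 |
|---|---|---|---|---|
| Bilirubin in the Hy's law test | Total; direct if Gilbert's | Total; direct if Gilbert's | Total, all patients | Total, all patients |
| Other-causes clause | Yes | Yes | No | Yes |
| Count of abnormal bilirubin | Total; the Gilbert's sentence may or may not extend to it | Total, no exception | Total >2×ULN, no exception | Not covered |

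For Hy's law the conflict is explicit: 11.7 has the exception and both SAP sections lack it. For the plain count of raised total bilirubin, 11.7 and the SAP agree. Only the synopsis can be read as asking for direct bilirubin there.

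**Step 2. Does the other-causes clause replace the rule?** Protocol 11.7 carries the clause and the direct-bilirubin rule in the same sentence, so there the clause was not treated as sufficient. It is also missing from SAP 19.4, which defines the tabulation.

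**Step 3. Scale.** The documents supply N = 300 (Protocol 6.2, SAP 3.1). Everything else is assumed, because they give no Gilbert's prevalence and no rates for these laboratory values. Protocol 10.2.11.1 reports 7 bempedoic acid patients with confirmed ALT and/or AST above 3×ULN up to the end of Phase 2. That shows such rises occur, but no denominator is given, so no rate follows.

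Assumptions:
- g, share with Gilbert's disease: 1% to 10%, that is 3 to 30 patients
- t, share of those with an on-study total bilirubin above 2×ULN and normal direct bilirubin: 10% to 50%
- a, share with ALT or AST above 3×ULN, independent of Gilbert's status: 0.5% to 2%

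Expected Gilbert's-only Hy's law flags = 300 × g × t × a, and P(at least one) = 1 − (1 − g·t·a)^300.

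| g | t | a | Expected flags | P(at least one) |
|---|---|---|---|---|
| 1% | 10% | 0.5% | 0.0015 | 0.0015 |
| 5% | 30% | 0.5% | 0.0225 | 0.022 |
| 5% | 30% | 2% | 0.09 | 0.086 |
| 10% | 50% | 2% | 0.30 | 0.26 |

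For the total-bilirubin row, expected entries due to Gilbert's disease alone = 300 × g × t. This runs from 300 × 0.01 × 0.10 = 0.3 to 300 × 0.10 × 0.50 = 15, with P(at least one) from 0.26 to about 1.00.

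The missed-case direction is not quantified, since nothing in the documents bears on its frequency.

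**The case against.** **The total-bilirubin row follows the protocol body.** A reader might infer that this row also breaks the protocol. Section 11.7 counts abnormal total bilirubin with no exception, and the synopsis sentence comes directly after the Hy's law sentence, so it may apply to Hy's law alone. The documents do not support calling this row a contradiction. It needs annotation, not a change of analyte.

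**Safeguards remain.** The SAP calls these cases potential and lists them. Protocol 10.2.11.3.2 requires total and direct bilirubin in the repeat panel after an ALT or AST above 3×ULN. SAP 19.4 summarises the laboratory parameters of Protocol 10.1.6.1, which include direct bilirubin. Over-flagging at a screening step is the cautious error. All of this stands, and a careful reader could resolve a flagged case by hand. It does not help a patient who was set aside under 19.4.1, and it leaves the tabulated count on a different definition from the protocol's.

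**The table shells are not available.** SAP 8 says they fix the format and content of the outputs, so a Gilbert's footnote there cannot be ruled out. That lowers certainty about the final tables but does not alter the SAP's written definition.

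**A Gilbert's flag may not exist ready-made.** This is fair. No eCRF field is named for it, and the reflex indirect bilirubin is not in Protocol Table 4.

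**Conclusion.** The point holds for the Hy's law definition. The SAP replaces a stated protocol rule with total bilirubin for everyone, gives no reason, and takes precedence. The post-hoc addendum of 18 December 2018 adds a liver function summary but does not restore the rule.

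The expected effect is small: 0.0015 to 0.30 Gilbert's-only potential Hy's law flags in the trial, on assumed inputs and assumed independence of Gilbert's status and enzyme rises. The count is most likely unchanged.

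Two stronger readings are tempting and not supported:
- **That the counts will be wrong.** Misclassification needs an enrolled patient with Gilbert's disease who crosses 2×ULN and also has the enzyme rise. The documents do not show that this will happen.
- **That one such case would alter the hepatic safety conclusion, or what the DMC sees.** A false case would need explaining, but the conclusion is not tied to a count, and SAP 19 plans no between-group safety tests by default. The DMC list in SAP Appendix 3 includes a laboratory abnormality table (14.3.2.9) whose contents are not shown, and no Hy's law table.

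The change is worth making because it restores the sponsor's own rule at little cost.

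**What to change.** 1. **Hy's law (SAP 19.4 and 19.4.1).** For patients with Gilbert's disease, apply the >2×ULN test to direct bilirubin in both the potential Hy's law table and the listing, as Protocol 11.7 states. Use total bilirubin for all others. Define Gilbert's disease as a recorded history or a consistent reflex test at screening, and flag it in the listing.
2. **Total-bilirubin row (SAP 19.4).** Keep total bilirubin. Footnote the patients with Gilbert's disease, or show them separately, with their direct bilirubin.
3. If total bilirubin for everyone is intended, say so and justify the departure from Protocol 11.7.

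The addendum records that the planned analyses are complete and the study unblinded. At this stage the change would be a further addendum, labelled as made after unblinding; it would apply a rule already in the protocol.

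**Cost.** A few sentences, one programming condition and a listing column. Protocol Table 4 already includes direct bilirubin in the chemistry panel. The real work is deriving the Gilbert's flag from medical history and the screening reflex results, after checking that those results are in the database.

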**19.4.1. LABORATORY REFERENCE RANGES AND MARKEDLY ABNORMAL CRITERIA**

Quantitative laboratory measurements will be compared with the relevant laboratory reference ranges in SI units and categorized as:

- Low: Below the lower limit of the laboratory reference range.
- Normal: Within the laboratory reference range (upper and lower limit included).
- High: Above the upper limit of the laboratory reference range.

In addition to the high and low quantitative laboratory assignments, Hy’s law criteria (≥3 × ULN for either ALT or AST, with accompanying total bilirubin >2 × ULN in the absence of other known causes) will be used to identify potential Hy’s law cases.

[REDACTED]

Version Number: 1.7  
 Version Date: 21Mar2018

[REDACTED]

